4.5 Methods to Protect Participant Privacy

The following are the planned procedures for effectively protecting against and minimizing loss of participant privacy:

1. Study visits will be conducted in private rooms.
2. Each participant will be given a unique study identification number and data will not include any of the participant's PHI.
3. All participant-identifying information will be stored and managed on a secured database server or in a locked cabinet. If on a database, the information will be password protected.
4. Participant confidentiality will be maintained in accordance with Health Insurance Portability and Accountability Act (HIPAA) regulations.
5. Only the PI, study personnel, and laboratory personnel approved by the IRB and authorized to view PHI will have access to the information.
6. PHI will not be used during discussion, presentation or publication of any research data.
7. Files containing PHI data collected for recruitment and screening purposes will be kept in locked, secured filing cabinets accessible only to designated study personnel (research assistants and investigators)

4.6 Minimization of Bias

This study is designed as a double-blind intervention so neither staff nor participants are aware of their assigned intervention arm. Additionally, to minimize analyst bias, biomarkers will be de-identified and analyzed by technicians unfamiliar with the participants or study phase.

4.7 Maximizing Compliance and Minimizing Attrition

At the start of an individual's study participation, he/she may be given a schedule of their study visits if requested. Visits will be scheduled at a time of day that the participant determines is most convenient for them, and will be repeated at the same time for each visit if possible. Transportation will be provided for each visit as needed, snacks will be available, and stipends will be provided for each study milestone. If necessary/requested, reminder calls will be made to participants approximately 2 days prior to study visits.

Participants will be tracked throughout their enrollment. Each study visit will be documented. Some study visits will be followed with a brief telephone check-in to ask the participant questions about compliance, adverse effects, and their experience during the most recent visit. All calls to the participant and their feedback will be carefully tracked. Notes that may facilitate compliance, such as "call before 10 am," etc., will be kept in participant files.

We will employ specific strategies to maximize participation and compliance:

- **Positive Framing about Benefits:** Information will be presented in terms of the possible gains rather than the avoidance of losses as this is a more effective motivational approach.
- **Feedback and Recognition of Progress:** Participants will be acknowledged throughout their participation and will be recognized for their contributions to the study. We will remain in close contact with individuals throughout their participation with follow-up calls each month.
- **Incentives and Rewards:** Participants may receive snacks at each visit, cards for achieving milestones, such as birthdays, holidays, etc.; and certificates of completion.

CHAPTER 5. RESEARCH METHODS

5.1 Participant Visit Schedule

Study visits will take place at the Clinical Research Laboratory at HRC, Roslindale, MA, an HRC-affiliated housing site, or at the participants home or via telephone (if possible). This study includes up to 7 visits. Participant eligibility will be determined during an in-person screening. If eligible and interested, the participant will be asked to continue with additional study visits. The Week numbers are approximate in order to allow for flexibility in scheduling (e.g., one participant may be on the intervention for 28 days, while another may be on the intervention for 31 days). The assessments/activities for each study visit are outlined below.

Visits	Assessments at Each Visit
Telephone Screening	We will assess: 
1. Sleep Behaviors (e.g., Insomnia Severity Index)2. Medication use (e.g., sleep aids)*3. Medical History4. Other exclusion criteria 
*If individuals currently use certain sleep aids (e.g., melatonin), but are willing and able to avoid their use during the study, participants will be asked to avoid the use of the sleep aid for approximately 2-3 weeks before continuing with the study

Week 0 (Visit 1)	We will perform/assess: 
1. Informed Consent/Assessment of Understanding2. Medical History3. Health Behaviors4. Substance/Alcohol Use5. Social Network6. Height7. Weight 
If eligible, participants will be asked to:
 
1. Fill out a 3-day dietary record in the week prior to next visit2. Avoid consumption of certain foods, beverages, and supplements/medications (e.g., cherries, alcohol, and sleep aids) for the entire duration of the study.

	3. Wear a digital sleep sensor (e.g, Garmin Watch) every day/night for the duration of the study and keep a sleep diary of time they went to bed and got out of bed for each night.
Week 1 and Week 8 (Visit 2 and 5)	
Assessments/Activities:
 
 1. Turn in Diet Records 2. Symptoms 3. Vitals 4. Weight 5. Sleep Quality 6. Blood Draw and Urine Sample for Biomarker 7. Depressive Symptoms 8. Stress 9. Pain 10. Additional Relevant Questionnaires 
Participants will:
 
 1. Continue to wear the digital sleep sensor every day/night and maintain sleep diary 2. Start consuming assigned intervention product
Within the first 5 days of starting each intervention arm, participants will be called to confirm there is no impact of the timing of juice impact on sleep quality. If a participant discloses that they are noticing lower than usual sleep quality after consuming the juice, the timing of the dose will be modified to mitigate any negative effects.	
Week 3 and Week 10 (Visit 3 and 6)	
Assessments/Activities:
 
 1. Symptoms 2. Related Sleep Factors 3. Depressive Symptoms 4. Stress 5. Pain 
Participants will:
 
 1. Continue to wear the digital sleep sensor every day/night and maintain sleep diary 2. Continue consuming assigned intervention product 3. Fill out a 3-day dietary record in the week prior to next visit
Week 5 and Week 12 (Visit 4 and 7)	
Assessments/Activities:
 
 1. Turn in Diet Records 2. Symptoms 3. Related Sleep Factors 4. Vitals 5. Weight 6. Sleep Quality 7. Blood Draw and Urine Sample for Biomarkers 8. Depressive Symptoms 9. Stress 10. Pain 11. Additional Relevant Questionnaires 12. Compliance 
*If Week 5, participants will continue to wear the digital sleep sensor every day/night

Week 7 (No Visit)	
Participants will be asked to:
 
 1. Continue to wear the digital sleep sensor every day/night and maintain sleep diary 2. Fill out a 3-day dietary record in the week prior to next visit

5.2 Study Visits and Assessments

A summary of study visits and assessments is provided in the table below. Given that a primary goal of this pilot study is feasibility, we will allow for flexibility for the administration of some assessments at visits, as long as these changes do not impede the scientific interpretation.

Planned Study Assessments at Each Visit

Visit	1	2	3	4	-	5	6	7
-------	---	---	---	---	---	---	---	---

	Week 0	Week 1	Week 3	Week 5	Week 7	Week 8	Week 10	Week 12
Screening	X							
Update Medical History	X							
Health Behaviors and Social Network	X							
Relevant Symptoms		X	X	X		X	X	X
Vitals		X		X		X		X
Height	X							
Weight	X	X		X		X		X
Sleep Quality		X		X		X		X
Sleep Quantity (via Garmin Watch)	X	X	X	X	X	X	X	X
Related Sleep Factors			X	X			X	X
Proposed Biomarkers		X		X		X		X
Depressive Symptoms		X	X	X		X	X	X
Stress		X	X	X		X	X	X
Pain		X	X	X		X	X	X
3-Day Diet Record	X			X	X			X
Compliance				X		X		X

Eligible participants will be asked to avoid consumption of tart cherry products, as well as supplemental forms of flavonoids, magnesium, and tryptophan for the entire study in order to isolate the effects of our intervention on the proposed outcomes. They will also be advised to avoid intake of foods, beverages, and medicines that may impact sleep (e.g., alcohol, caffeine, sleep aids, medications that induce drowsiness). Participants will undergo a 1-week (approximately 7 nights) pre-intervention assessment of sleep quantity via a digital wearable device that measures aspects like sleep quantity and physical activity (e.g., Garmin Watch™), which will serve as the baseline assessment for these measures. Furthermore, participants will be asked to record the time they went to bed and the time they got out of bed (i.e., sleep diary) for the entire study. Participants will also be asked to complete a 3-day diet record. At the baseline visit, medical history, and basic anthropometric information will be collected. Participants will provide a urine sample and fasted blood samples for biomarker analyses, complete questionnaires (e.g., sleep quality, mood, etc.) and have their vitals measured. Blood samples will be collected between 8-10 am, to avoid the impact of time of day on markers. After randomization to one of the intervention arms, participants will be asked to consume their intervention product twice per day for approximately 4 weeks, while also wearing the digital sleep sensor. Half of the intervention dose is intended to be consumed at approximately 5 pm and the other approximately 1 hour before bedtime. Individuals may receive reminder messages via their digital wearable device or via email/text to remind them about their study responsibilities (e.g., charging their devices etc). All assessments that were performed at baseline will be repeated approximately 4 weeks later at follow-up (e.g., urine sample, blood draw, questionnaires). After approximately 2 weeks of a washout period (to reduce the impact of a carry-over effect from the intervention), participants will complete the same schedule with the other intervention product.

Telephone Pre-screen (~30 minutes): Volunteers will be asked about demographic information, sleep behaviors/insomnia, medication/supplement use, any past/present medical conditions and/or treatments, as well as other exclusionary criteria.

Medical History: Participants will be asked to disclose any existing or previous medical conditions via self-report.

Insomnia Severity Index: The insomnia severity index will be administered to determine eligibility. Individuals scoring 10 points or higher will be eligible.

Screening Visit (Week 0; ~60 minutes): Individuals deemed potentially eligible via the phone screen will complete an in-person screen. All screening assessments will be administered by trained research assistants. Eligible and interested participants will read and sign an informed consent form approved by HRC's IRB. A medical history and health behaviors questionnaire will be completed which will ask about current/past conditions, medications, etc. Validated questionnaires that assess substance and alcohol use, as well as social connectedness will be administered. The participant's height and weight will be collected.

Informed Consent: In order to participate in this study, all interested and eligible participants will be required to provide informed consent. They will be given ample time to ask any questions about the study. A trained research staff will answer any questions and if the individual is interested in participating in the study, they will be offered to sign the informed consent form. When the staff member is confident that the participant is completely familiar with the document and understands all the aspects of the informed consent form, it will be signed by the participant in the presence of the staff member, and then be signed by the staff member. All consent forms will be double-checked to make sure they are properly signed and dated. Copies of completed consent forms will be given to the participant and the original signed document will be kept on file at the Hinda and Arthur Marcus Institute for Aging Research. As a part of the informed consent process, potential participants will be clearly informed that this intervention is not a treatment option for sleep, but rather studying feasibility of a dietary strategy for health. If seeking a treatment, they will be directed to their primary care.

Medical History/Health Behaviors: Additional measures to characterize the participants will include existing or previous medical conditions, medication use, smoking status, use of drug, use of alcohol etc.

Drug Abuse Screening Test (DAST) will evaluate drug use. DAST will be administered to participants and individuals who scores >2 points, will be excluded.^{35,36}

Alcohol Use Disorders Identification Test (AUDIT) will be administered to participants to evaluate alcohol use. For this study, we will administer a shortened version (AUDIT-Consumption) by asking only the first three questions from the full questionnaire. Individuals scoring ≥ 4 points will be excluded.^{33,34}

Social Network: Subjective perception of social support and connectedness will be evaluated using a validated questionnaire.³⁷

Height/Weight will be measured.

1. Height will be measured using a stadiometer.
2. Weight will be measured using a digital Health-o-meter scale.

If eligible, all participants will be asked to avoid consumption of certain foods (e.g., tart cherries) and fill out a 3-day diet record to estimate nutrient intake in the week prior to their next visit. Participants will also be asked to wear the digital sleep sensor all day and night for the remainder of the study. They will also be given a log to record the time they go to bed and the time they get out of bed for the duration of the study.

3-Day Diet Records: Diet records (consisting of 2 weekdays and 1 weekend day) will be reviewed by research staff for accuracy and completeness. Records will be entered into a dietary analysis program (e.g., Nutrition Data System for Research) to estimate dietary intake of nutrients.

Sleep Quantity: Sleep quantity will be assessed subjectively and objectively. For the subjective measure, participants will be given a daily log or journal to document aspects of their sleep (e.g., time of sleep onset, time of rising, number of disturbances, self-rated satisfaction with sleep). Participants are asked to complete this log every day they are in the study. To objectively measure sleep quantity,

participants are asked to wear a digital device that measures sleep quantity. Participants will be asked to wear the device throughout the intervention to objectively capture quantitative aspects of sleep (e.g., time in bed, number of times awake). This device has the capacity will be connected to the participants phone via free, downloadable applications. Reminders may be sent via the device or via email during the study (e.g., reminder to charge device, reminder to open up app to sync data, etc).

Week 1 and Week 8 Visits (~60 minutes): Participants will be asked to turn in their 3-day diet records. Relevant symptoms, weight, vitals, sleep quality, depressive symptoms, stress, pain and any additional relevant questionnaires will be evaluated. Additionally, up to 16 mL of blood will be taken to measure biomarkers in serum and a morning urine sample will be collected. Participants will be given their allotment of intervention products to consume each day and continue to wear their Garmin Watch.

Vital Signs (e.g., body temperature, pulse, and seated blood pressure) will be measured. After 3-5 minutes of rest, seated blood pressure will be measured twice with an automated cuff.

Sleep Quality will be evaluated using a validated self-report questionnaire the Pittsburgh Sleep Quality Index (PSQI).³⁸

Relevant Symptoms including gastrointestinal distress, appetite, pain etc., will be collected by self-report.

Blood (approximately 16 mL) will be collected by a trained phlebotomist using sterile procedures. Blood will be processed and stored at -80 degree C for future analyses. Batch analyses of planned biomarkers (e.g., kynurenine/tryptophan ratio and select inflammatory markers (e.g., C-reactive protein, interleukin-6, etc.) will be measured by a reputable lab (e.g., Quest or collaborators at the University of Connecticut).

Spot Urine (approximately 30 mL) will be collected, processed, and stored at -80 degree C for future analyses. We will aim to collect urine in the morning hours between 8-10 am to avoid the influence of the circadian rhythm on cortisol. Batch analyses of planned biomarkers (e.g., cortisol and melatonin.) will be measured by a reputable lab (e.g., Quest or collaborators at the University of Connecticut).

Depressive symptoms will be evaluated using a validated self-report questionnaire (e.g., the Center for Epidemiological Studies Depression Scale (CES-D),³⁹ the CESD-revised (CESD-R)⁴⁰ version, and/or the Patient Health Questionnaire-9 (PHQ-9)³⁶).

Stress will be evaluated by the validated 10-item questionnaire, the Perceived Stress Scale.⁴¹

Pain will be evaluated via a validated 24-item questionnaire, the Geriatric Pain Measure.⁴²

Additional Questionnaires will be administered to evaluate other aspects that are relevant to sleep to help characterize our study population (e.g., validated self-report questionnaires that measure anxiety, affect etc.)

Compliance: Compliance with our dietary intervention will be evaluated throughout the study. Participants will be asked to log consumption of their juice and keep all of their empty bottles. Participants will return all remaining empty/full bottles to estimate number of intended doses that were consumed.

Within the first 5 days of starting each intervention arm, participants will be called to confirm there is no impact of the timing of juice impact on sleep quality. If a participant discloses that they are noticing lower than usual sleep quality after consuming the juice, the timing of the dose will be modified to mitigate any negative effects.

Week 3 and Week 10 (~30 minutes): These visits may take place over the phone. They will include an evaluation of relevant symptoms, related sleep factors, depressive symptoms, stress, pain, and compliance. Participants will be asked to fill out a 3-day diet record to estimate nutrient intake in the week prior to their next visit.

Related Sleep Factors: In addition to the assessment of sleep quality and quantity, we will also collected data about factors that are known to affect sleep (e.g., use of alcohol, room temperature via sensor given to participants), that may occur to help characterize or understand unexpected/unusual patterns in the data.

Week 5 and Week 12 Visits (~60 minutes): Participants will be asked to turn in their 3-day diet records. Relevant symptoms, weight, vitals, sleep quality, related sleep factors, depressive symptoms, stress, pain and any additional relevant questionnaires will be evaluated. Additionally, up to 16 mL of blood will be taken to measure biomarkers in serum and a morning urine sample will be collected.

At Week 7, participants will be asked to fill out a 3-day diet record to estimate nutrient intake in the week prior to their next visit. This is not an official visit.

At the end of the intervention (e.g., Week 12 Visit), participants will be asked to provide feedback via open ended questions on their experience during the intervention. They will also be asked if they would be willing to consume this intervention long-term and to guess as to which arm they were on in the beginning and ending of the intervention.

Optional Study Assessments: Participants will also have the option to partake in two optional study assessments as described below. These optional study assessments allow for further investigations of potential mechanisms relevant to sleep, including analysis of phenolic metabolites in urine and analysis of the gut microbiota in fecal samples.

24 Hour Urine Sample: If participants are willing, they will be asked to provide a 24 hour urine collection instead of the planned spot urine collection. This requires individuals to collect all of their urine for the 24 hours preceding select study visits using a provided urine container. Urine will be processed and frozen until analysis. Regardless of whether participants opt for the spot or the 24 hour urine sample, batch analyses of planned urinary biomarkers (e.g., cortisol and melatonin) will be measured by a reputable lab (e.g., Quest or collaborators at the University of Connecticut). The 24 hour urine sample will also be used to evaluate phenolic metabolites. Briefly, urine samples acidified with formic acid will be purified via solid phase extraction to isolate gut-microbially generated phenolic acid metabolites (and their subsequent phase II hepatic conjugates). Purified samples will be analyzed using LC-MS/MS with a triple-quad mass spectrometer to quantify metabolites by their specific parent to daughter ion mass transitions. Targeted metabolomics quantifies ~60 phenolics, gut microbially generated phenolic acid metabolites, and hepatic phase II metabolites of absorbed phenolics and phenolic acids.

Fecal Sample: If participants are willing, they will be asked to collect at least 1 (no more than 3) separate fecal samples before select visits. Samples will be collected as is, in a sterile collection tube without any preservation medium that will be provided to participants. There will be a collection for select visits as indicated below. Participants will temporarily store the self-collected fecal samples in their own freezer (-17°C), and then transported to the lab at HSL for sample processing and long-term storage. Fecal microbiota will be analyzed using whole genome sequencing (WGS) to obtain a holistic representation of the microbes in the gut. WGS was chosen because it enables identification of microbes down to specific species or strain of bacteria whereas other methods only identify the genus level and avoid biases common with 16S rRNA sequencing. A reputable lab (e.g., the Microbial Omics Core at the Broad Institute) will perform the DNA extraction from fecal samples and WGS library construction and sequencing using NEBNext Ultra FS II (2x150bp sequencing chemistry to a minimum depth of 3 million reads per sample). Fastq sequences will be processed and analyzed by a reputable lab/core (e.g., the Harvard Chan Microbiome Analysis Core).

Optional Study Assessments

Visit	1	2	3	4	-	5	6	7
	Week 0	Week 1	Week 3	Week 5	Week 7	Week 8	Week 10	Week 12
24 Hour Urine Collection	X			X	X			X
Fecal Sample	X			X	X			X

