3.1 Study Objectives and Aims

The **overall goal** of this study is to determine feasibility of a tart cherry juice intervention in older adults, and generate preliminary data of outcomes and mechanisms related to sleep. We propose a 2-arm randomized, double-blind, cross-over study in 20 older adults with self-reported insomnia. Participants will consume 240 mL of tart cherry juice or placebo (calorically matched to the tart cherry juice beverage, but theoretically devoid of melatonin, tryptophan, magnesium and flavonoids), twice/evening for approximately 4 weeks in a randomly assigned order. The aims are:

Aim 1: Determine the feasibility of recruiting individuals for and implementing a 4 week tart cherry juice intervention in older adults with self-reported insomnia. Hypothesis: Recruitment for and implementation of a tart cherry juice intervention in older adults with self-reported insomnia is feasible.

Aim 2: Generate preliminary data for sleep quantity, sleep quality, and relevant biomarkers in older adults with self-reported insomnia enrolled in a double-blind randomized placebo controlled tart cherry juice intervention. Hypothesis: Intake of tart cherry juice tends to increase sleep quantity (via sleep monitoring device), sleep quality (via validated questionnaire, e.g., the Pittsburg Sleep Quality Index) urinary melatonin, and serum serotonin, as well as decrease urinary cortisol and serum inflammatory markers.

Exploratory Aim: Explore the impact of tart cherry juice intake on sleep-related factors that may be impacted by the Aim 2 biomarkers in older adults. Hypothesis: Intake of tart cherry juice for 4 weeks results in changes in mood, stress, and pain.

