3.6 Study Intervention Products

Tart cherry juice will be purchased from a commercial supplier (e.g., Shoreline Fruit™). Shoreline Fruit will be responsible for preparing and bottling the tart cherry juice. Frozen or fresh tart cherries will be juiced and bottled according to the manufacturers normal processing. The intervention products will be prepared following proper food safety/handling protocols and the bottles. The bottles of tart cherry juice will be labeled with a letter, number or symbol, that distinguishes it from the placebo.

Unsweetened black cherry powder (e.g., Kool-aid™) will be purchased and used as the placebo. A reputable, established lab (e.g., Rutgers Food Innovation Center) will prepare the placebo, who will follow safe, good manufacturing practices. The placebo will be prepared to match the caloric/sugar content of the tart cherry juice. The Kool-aid has a similar taste and color, however does not contain significant amounts of our active ingredient (i.e., tart cherries) or active putative compounds (e.g., magnesium, melatonin, tryptophan, flavonoids). The placebo will be bottled in the same bottle type that the tart cherry juice is bottled in, however it will be marked with a letter, number, or symbol that differs from the one used to identify the tart cherry juice.

The key that decodes which of the letter/number corresponds with which product will be kept secure by an independent party (e.g., an individual at the Biostatistics and Data Sciences Core of the Marcus Institute). Thus, the participants, study staff, and analyzers of the data will be blinded to the letter/number that is used to identify the tart cherry juice vs the placebo. At the end of the data collection and data analysis, the study team will be unblinded. See §5.3 for further information on dietary intervention. Individuals will be provided with an allotment of the intervention products and additional bottles will be delivered by our study staff as needed.

CHAPTER 4 RECRUITMENT AND DATA COLLECTION

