5.4 Outcome Measures

Our primary endpoints are aspects of feasibility. Secondary endpoints include sleep quantity and quality, as well as sleep-related biomarkers (e.g., melatonin, serotonin, cortisol, inflammatory markers). Exploratory outcomes include sleep-related factors (e.g., mood, stress, pain). We will also explore other alternative outcomes.

Name	Type	Timeframe	Brief description
Recruitment Rate	Primary	Throughout the entire study	Number of individuals that need to be screened to be enrolled that are randomized to the intervention.
Attrition	Primary	Throughout the entire study	Number of individuals randomized that withdraw from the intervention in media res .
Compliance of Dose	Primary	Throughout the entire study	The number of intended doses consumed.
Ability to Collect Data	Primary	Throughout the entire study	The percentage of missing data points from electronic capture data devices.
Practicality	Primary	Throughout the entire study	Self-reported willingness to continue the dietary regimen after study completion.
Sleep Quantity	Secondary	Throughout the entire study	Individuals will be asked to wear a polysomnographic device (e.g., Garmin

			watch) to continuously measure aspects related to sleep quantity (e.g., total sleep time, time spent awake).
Sleep Quality	Secondary	Week 1, 5, 8, 12	The validated self-report questionnaire, the Pittsburgh Sleep Quality Index, which ranges from 0-21 points.
Melatonin	Secondary	Week 1, 5, 8, 12	Melatonin will be estimated by measuring the major urinary metabolite of melatonin, 6-sulphatoxymelatonin, utilizing a commercially available quantitative immunoassay.
Serotonin	Secondary	Week 1, 5, 8, 12	Serotonin production will be estimated by measuring the kynurenine/tryptophan ratio in blood collected from participants utilizing a commercially available quantitative immunoassay.
Cortisol	Secondary	Week 1, 5, 8, 12	Urinary cortisol will be estimated utilizing a commercially available quantitative immunoassay.
Inflammatory Markers	Secondary	Week 1, 5, 8, 12	A panel of several serum biomarkers related to inflammation (e.g., C-reactive protein, interleukin-6) will be measured in blood collected from participants utilizing a commercially available quantitative immunoassay.
Mood	Exploratory	Week 1, 3, 5, 8, 10, 12	A validated self-report questionnaire (e.g., the CES-D/CESD R, which ranges from 0-60 points or the PHQ-9, which ranges from 0-27 points)

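### Practicality, a primary feasibility measure, is described only as an end-of-study question about an unnamed drink, so the answer cannot be attributed to tart cherry juice

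*Combined protocol and SAP*

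**What the plan says.** Aim 1 in section 3.1 concerns the active product: "Determine the feasibility of recruiting individuals for and implementing a 4 week tart cherry juice intervention in older adults with self-reported insomnia".

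Section 5.4 lists five primary measures: recruitment rate, attrition, compliance of dose, ability to collect data, and practicality. Practicality is defined as "Self-reported willingness to continue the dietary regimen after study completion", with the whole study as its time frame. The only description of how it is collected is the closing paragraph on visits in section 5.2: "At the end of the intervention (e.g., Week 12 Visit), participants will be asked to provide feedback", and then "They will also be asked if they would be willing to consume this intervention long-term". The same paragraph asks participants to guess which arm they were on at the beginning and at the end. Neither the Week 5 list in section 5.1 nor the assessment table in section 5.2 contains a willingness item.

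Compliance of Dose is defined in section 5.4 as "The number of intended doses consumed". Section 5.2 has participants log their juice and adds: "Participants will return all remaining empty/full bottles to estimate number of intended doses that were consumed". Section 3.6 says of the placebo bottle that "it will be marked with a letter, number, or symbol that differs from the one used to identify the tart cherry juice". Section 5.1 allows period length to vary; for example, "one participant may be on the intervention for 28 days, while another may be on the intervention for 31 days".

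Sections 6.2 and 6.3 say that feasibility will be tabulated with 80% confidence intervals. They state no split by product and place the grading thresholds in the Manual of Procedures.

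**The concern.** In a crossover, every completer has had both drinks by the last visit. A willingness question asked then, without naming a drink or a period, may be answered about the last drink, the preferred drink, or the routine of two evening drinks in general. Section 4.2 randomizes the order, so some participants answer just after juice and others just after placebo.

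Feasibility is the primary outcome. Section 6.3 grades each metric as feasible, in need of modification, or not feasible, and section 8.6 makes a feasible result a condition for later trials. A grade for Practicality that partly reflects willingness to drink the placebo does not answer Aim 1. Most gaps in endpoint definition can be closed at the analysis stage. This one cannot, because what the participant had in mind is never recorded.

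**Working it through.** The plan gives no figure to reproduce for Practicality, so the check is one of timing, attribution and precision.

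**Timing (section 5.1).** Period 1 ends at Week 5 and period 2 at Week 12. For the juice-first sequence, the gap between the end of juice and the question is 12 − 5 = 7 weeks, of which the last 4 or so were on placebo.

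**How many are affected.** Planned N is 20 (sections 3.4 and 4.2). The allocation ratio is not stated. With 1:1 allocation and equal retention, 20 × 0.5 = 10 answer just after placebo and 10 just after juice.

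**What a single overall figure can hide.** Suppose that answers concern the last drink. With w the share whose last drink was juice, the observed proportion is w × p(juice) + (1 − w) × p(placebo). The rates below are illustrative.

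| w | juice 50%, placebo 90% | juice 90%, placebo 50% |
|---|---|---|
| 0.4 | 0.20 + 0.54 = 74% | 0.36 + 0.30 = 66% |
| 0.5 | 0.25 + 0.45 = 70% | 0.45 + 0.25 = 70% |
| 0.6 | 0.30 + 0.36 = 66% | 0.54 + 0.20 = 74% |

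A 40-point difference in willingness to drink the juice moves the overall figure by 0 to 8 points. At w = 0.5, 70% overall fits juice willingness from 2 × 0.70 − 1 = 40% up to 100%.

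**Can unblinding repair it?** Unblinding tells the analyst each participant's last drink. Splitting by last drink would then work only if every answer concerned that drink, which the question does not ensure. Even granting that, about 10 answers would concern juice. Asking after each period gives up to 20. Using exact (Clopper-Pearson) 80% intervals, since the plan does not name a method, and an illustrative 70% willing:

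- 7 of 10: 0.45 to 0.88, width about 0.44
- 14 of 20: 0.53 to 0.83, width about 0.30

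**Early withdrawal.** Section 3.4 expects that not all 20 may complete. A participant who finishes juice first and leaves in period 2 may never reach the end-of-study question. A Week 5 question would already have that participant's answer.

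**Compliance of Dose.** Two doses a day give 2 × 28 = 56 scheduled doses in a 28-day period and 2 × 31 = 62 in a 31-day period. The same count of 56 is 56/56 = 100% or 56/62 = 90.3%. The 28 and 31 days are the protocol's examples, not limits. Compliance is collected at the end of each period (Weeks 5 and 12), with a log and coded bottles. Doses by product can therefore be derived after unblinding.

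**The case against.** The best defence is that section 5.4 defines Practicality by the regimen rather than the juice. The regimen has the same volume and timing on both products, and the placebo is matched for color, calories and sugar (section 5.3). The burden of two evening drinks is a fair feasibility target, and a future trial would need people to tolerate the placebo too. The e.g. before Week 12 and the whole-study time frame in section 5.4 also leave some room on timing. The Manual of Procedures is not available and may say more. Aim 1 is descriptive.

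Much of this is fair, but it does not remove the gap. Aim 1 names the juice, and a measure of the routine alone leaves out acceptance of the product itself. No timing other than the end of the study is described. Sections 6.2 and 6.3 assign the thresholds to the manual, and a threshold does not say which drink an answer concerned. The arm-guess item separates the two periods, but the willingness item beside it does not.

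A reader might also infer three stronger points, which the documents do not support:

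- **That doses are pooled over both products.** Nothing says so, and the planned logs, returns and coded bottles allow a split.
- **That the primary feasibility measures in general are not tied to the juice.** The gap in wording is shown for two of five, and recruitment rate cannot be specific to a product.
- **That exactly half the answers follow placebo.** This needs 1:1 allocation and equal retention, and neither is stated.

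**Conclusion.** The point holds for Practicality. As described, the answer cannot be attributed to tart cherry juice, and unblinding cannot recover what it referred to. About 10 of 20 answers would follow placebo under 1:1 allocation and equal retention. The illustrative rates show that very different juice results can give the same overall figure. The conclusion rests on reading the question as asked only at the end of the study, which is the natural reading but is softened by the e.g. in section 5.2.

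For Compliance of Dose, only a definition gap remains: no denominator and no product are stated, but the planned data can supply both. The change to Practicality has to be made before participants pass Week 5. The compliance wording can be settled at any time before analysis.

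**What to change.** 1. Ask the willingness question at both Week 5 and Week 12, worded about the drink taken in the period just completed. Add it to the visit list in section 5.1 and the table in section 5.2.
2. In section 5.4, define Practicality as the proportion willing after the tart cherry juice period, with the placebo-period answer as comparator. Give its time frame as Weeks 5 and 12.
3. In section 5.4, state that Compliance of Dose is reported by product, as doses taken divided by doses scheduled between the actual start and stop dates.

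The cost is one extra question at an existing visit and a few lines of protocol wording. Participants stay blinded, because the question refers to a period and not to a named product; answers are assigned to juice or placebo after unblinding. No new data are needed for the compliance wording.
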